9.7.1.6.3 EXPLORATORY EFFICACY ANALYSES

Time to change of concomitant AD treatment will be analyzed similarly to that for time to conversion to dementia based on clinical diagnosis. Time to change of concomitant AD treatment is defined as time from randomization to the first dose increase and/or initiation of

treatment with AChEI or memantine after randomization. For subjects without any change of concomitant AD treatment by the end of study, the time to change of concomitant AD treatment will be censored at the date of last assessment of concomitant medication.

The proportion of subjects with any change of concomitant AD treatment at 24 months will be analyzed similarly to that for proportion of subjects with dementia diagnosis at 24 months.

The rate of change over time (mean slope) based on change from baseline in the NPI-10 item will be analyzed in a manner similar to that used for the rate of change over time (mean slope) based on change from baseline in the CDR-SB.

The analysis of the following exploratory efficacy endpoints will be performed to compare elenbecestat (E2609) versus placebo using the appropriate prespecified statistical methods including MMRM model, analysis of covariance model (ANCOVA), etc. For each exploratory efficacy endpoint, the treatment effect for elenbecestat (E2609) 50 mg per day versus placebo will be tested at a significance level of 2-sided alpha = 0.05.

- Change from baseline in NPI-10 item at 24 months
- Change from baseline in EQ-5D (subject self-reported, study partner self-reported, and subject measured by proxy) and QOL-AD (subject and study partner) at 24 months
- Change from baseline in Zarit's Burden Interview at 24 months

Additional analyses may be performed as needed.

9.7.1.7 Pharmacokinetic, Pharmacodynamic, Pharmacogenomic, and Other Biomarker Analyses

9.7.1.7.1 PHARMACOKINETIC ANALYSES

Safety Analysis sets will be used for individual elenbecestat (E2609) plasma and CSF concentration listings. The PK Analysis Set will be used for the summaries of elenbecestat (E2609) plasma and CSF concentrations.

A population PK approach will be used to characterize the PK of elenbecestat (E2609). The effect of covariates (ie, demographics) on elenbecestat (E2609) PK will be evaluated. The PK model will be parameterized for clearance (CL) and volumes of distribution. Derived exposure parameters such as AUC will be calculated from the model using the individual posterior estimate of CL and dosing history.

9.7.1.7.2 PHARMACOKINETIC-PHARMACODYNAMIC

The PK/PD relationship between CSF biomarker levels and plasma PK parameters or CSF concentrations of elenbecestat (E2609) will be explored graphically and any emergent relationship will be explored through population PK/PD modeling. These PK parameters include maximum observed concentration (C_{max}), and $AUC_{(0-24)}$ derived from the population PK model. The PK/PD relationship between plasma PK parameters and CSF concentrations of elenbecestat (E2609) with other biomarkers may also be explored using similar methods.

Additionally, the relationship between various PK parameters (eg, C_{max}) or CSF concentrations of elenbecestat (E2609) and CDR-SB at 24 months, and the relationship between various PK exposure parameters or CSF concentrations of elenbecestat (E2609) and the change from Baseline for 24 months in ADAS-cog₁₄, and the MMSE, will be explored graphically. Any emergent relationships will be explored through population PK/PD modeling. The relationship between exposure to elenbecestat (E2609) and most frequent AEs will also be explored.

9.7.1.7.3 PHARMACODYNAMIC, PHARMACOGENOMIC, AND OTHER BIOMARKER ANALYSES

The analysis of the biomarker endpoints defined as below will be performed to compare elenbecestat (E2609) versus placebo using the appropriate prespecified statistical methods including MMRM model, analysis of covariance model (ANCOVA), etc. These analyses will be conducted without adjustment for multiplicity or sequential testing. For each endpoint, the treatment effect for elenbecestat (E2609) 50 mg per day versus placebo will be tested at a significance level of 2-sided alpha = 0.05.

- Change from baseline in amyloid PET SUVR composite at 24 months for brain amyloid levels
- Change from baseline in CSF biomarkers t-tau and p-tau at 24 months
- Change from baseline in CSF amyloid biomarkers $A\beta(1-40)$, $A\beta(1-42)$, and $A\beta(1-x)$ at 24 months
- Change from baseline in total hippocampal volume at 12 and 24 months using vMRI
- Change from baseline in the preservation of connectivity on fMRI from predefined anatomical regions connectivity maps (eg, precuneus, inferior frontal sulcus)

The relationship between exposure (in CSF, plasma) of elenbecestat (E2609) with potential biomarkers of Alzheimer's disease as deemed appropriate will be evaluated using appropriate statistical model with the continuous changes in biomarker at 24 months as response variables and exposure variables (in CSF, plasma) of elenbecestat (E2609) as independent variables.

9.7.1.8 Safety Analyses

Evaluations of safety will be performed on the Safety Analysis Set. The incidence of AEs, out-of-normal-range laboratory safety test variables, abnormal ECG findings, and out-of-range vital signs, suicidality, results of the sleep questionnaire, along with change from baseline in laboratory safety test variables, ECGs, and vital sign measurements will be summarized by treatment group.

9.7.1.8.1 EXTENT OF EXPOSURE

The Duration of exposure to study drug will be summarized as cumulative extent of exposure in categories with 3-month increment. The cumulative number and percent of subjects in each applicable exposure category will be presented by treatment group. Duration of exposure will be summarized using descriptive statistics as well as by 3-month duration categories using counts. The number and percent of subjects within each duration category

will be presented by treatment group. Overall exposure (number of subject-months) is defined as summation over all subjects' exposure durations and will be summarized by treatment group.

9.7.1.8.2 ADVERSE EVENTS

The AE verbatim descriptions (investigator terms from the eCRF) will be classified into standardized medical terminology using the Medical Dictionary for Regulatory Activities (MedDRA). AEs will be coded to the MedDRA (Version 19.0 or higher) lower level term closest to the verbatim term. The linked MedDRA PT and primary system organ class (SOC) are also captured in the database.

A TEAE is defined as:

- An AE that emerges during treatment within 4 weeks of the last dose of study drug, having been absent at pretreatment (Baseline) or
- Reemerges during treatment, having been present at pretreatment (Baseline) but stopped before treatment, or
- Worsens in severity during treatment relative to the pretreatment state, when the AE is continuous.

Only those AEs that are treatment-emergent will be included in summary tables. All AEs, treatment-emergent or otherwise, will be presented in subject data listings.

The TEAEs will be summarized by treatment group on the Safety Analysis Set. The incidence of TEAEs will be reported as the number (percentage) of subjects with TEAEs by SOC and PT. A subject will be counted only once within an SOC and PT, even if the subject experienced more than 1 TEAE within a specific SOC and PT. The number (percentage) of subjects with TEAEs will also be summarized by maximum severity (mild, moderate, or severe). The number (percentage) of subjects with TEAEs will also be summarized by relationship to study drug (Yes [related] and No [not related]).

The number (percentage) of subjects with treatment-related TEAEs will be summarized by SOC and PT. Treatment-related TEAEs include those events considered by the investigator to be related to study drug. The number (percentage) of subjects with treatment-related TEAEs will also be summarized by maximum severity (mild, moderate, or severe).

AEs will be summarized by the following subgroups: region, prior treatment with AChEIs or memantine (no or yes), and clinical subpopulation (MCI due to AD or the early stages of AD).

The number (percentage) of subjects with TEAEs leading to death will be summarized by MedDRA SOC and PT for each treatment group. A subject data listing of all AEs leading to death will be provided. The number (percentage) of subjects with treatment-emergent SAEs

will be summarized by MedDRA SOC and PT for each treatment group. A subject data listing of all SAEs will be provided. The number (percentage) of subjects with TEAEs leading to discontinuation from study drug will be summarized by MedDRA SOC and PT for each treatment group. A subject data listing of all AEs leading to discontinuation from study drug will be provided.

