9.3.3 Removal of Subjects from Therapy or Assessment

The investigator may withdraw the subject from the study at any time for safety or administrative reasons. The subject may stop study drug or withdraw from the study at any time for any reason.

Absolute lymphocyte count from the hematology and differential panel will be monitored during the study. ALC will be derived from the CBC with differential representing the normal lymphocytes (with atypical lymphocytes removed and presented as a separate count if they are present) and calculated by the white blood cell count \times percentage of lymphocytes. (revised per Amendment 01) Should a subject develop a Grade 2 or greater lymphocytopenia (less than $800/\text{mm}^3$), this should be confirmed as soon as possible but no later than within 5 days with a repeat test of absolute lymphocyte count. If confirmed, study drug administration should be interrupted for a minimum period of 2 weeks and for a maximum period of 4 weeks. Restart of study drug may take place only when absolute lymphocyte count returns to greater than LLN. Absolute lymphocyte count will be measured 4 weeks after restart of study drug. Subsequent measurements of absolute lymphocyte counts will follow the schedule of assessments (Table 3) and any results showing a Grade 2 or greater lymphocytopenia (less than $800/\text{mm}^3$) should be handled as above. If a 2nd occurrence of Grade 2 or greater lymphocytopenia (less than $800/\text{mm}^3$), that is confirmed on repeat testing, occurs within 6 months, then the subject should be discontinued permanently from the study drug.

Subjects who develop moderate or severe hepatic impairment during the study must discontinue study drug. (revised per Amendment 01)

Subjects who discontinue study drug early must complete the ED Visit (within 7 days of the last dose of study drug) and the Follow-Up Visits (1 and 3 months after the last dose of study drug). These Follow-Up Visits will be conducted to monitor efficacy and safety parameters after early withdrawal from the study or discontinuation of study drug.

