9.5.1.5.1 ADVERSE EVENTS AND EVENTS ASSOCIATED WITH SPECIAL SITUATIONS

An AE is any untoward medical occurrence in a subject or clinical investigation subject administered an investigational product. An AE does not necessarily have a causal relationship with the medicinal product. For this study, the study drug is elenbecestat (E2609).

The criteria for identifying AEs in this study are:

- Any unfavorable and unintended sign (including an abnormal laboratory finding), symptom, or disease temporally associated with the use of an investigational product, whether or not considered related to the investigational product (Note: Every sign or symptom should not be listed as a separate AE if the applicable disease [diagnosis] is being reported as an AE)
- Any new disease or exacerbation of an existing disease
- Any deterioration in nonprotocol-required measurements of a laboratory value or other clinical test (eg, ECG or x-ray) that results in symptoms, a change in treatment, or discontinuation of study drug
- Recurrence of an intermittent medical condition (eg, headache) not present pretreatment (Baseline)
- An abnormal laboratory test result should be considered an AE if the identified laboratory abnormality leads to any type of intervention, withdrawal of study drug, or withholding of study drug, whether prescribed in the protocol or not.

All AEs observed during the study will be reported on the eCRF. All AEs, regardless of relationship to study drug or procedure, should be collected beginning from the time the subject signs the study ICF through the last visit (Visit 15, as shown in [Table 3](#)). Subjects who fail screening primarily due to AE(s) must have the AE(s) leading to screen failure reported on the Screening Disposition eCRF and the Adverse Event eCRF. SAEs will be collected for 12 weeks after the last dose.

Abnormal laboratory values should not be listed as separate AEs if they are considered to be part of the clinical syndrome that is being reported as an AE. It is the responsibility of the investigator to review all laboratory findings in all subjects and determine if they constitute an AE. Medical and scientific judgment should be exercised in deciding whether an isolated laboratory abnormality should be classified as an AE. Any laboratory abnormality considered to constitute an AE should be reported on the Adverse Event eCRF.

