A subject with any skin rash of moderate to severe intensity, or any rash lasting more than 72 hours regardless of severity (with the exception of oral or genital herpes as described in the next paragraph), will be discontinued from study drug and a dermatologic consult will be requested regardless of whether the rash is considered drug related or due to other causes. For cases where the investigator suspects a drug rash, regardless of severity, the subject will be discontinued from study drug, a dermatologic consult will be requested, and a skin biopsy will be performed to confirm the diagnosis. The skin rash will be treated as per standard care and will be followed up until resolution regardless of etiology or severity.

Subjects who develop moderate to severe oral or genital herpes should be discontinued from study drug. Subjects who develop a mild case of oral or genital herpes may remain on study drug even if the event lasts more than 72 hours.

Neurologic Examination

A full neurologic examination (including general status, cranial nerve function, motor system, coordination/cerebellar function, reflexes, and, sensory system) will be performed at Screening and at Visit 13 (or ED). During the randomization phase, neurologic examinations will be performed at regular intervals as shown in [Table 3](#) and will focus on new symptoms and signs which will then alert the investigator to consider the occurrence of new CNS pathology. Examples of neurologic symptoms and signs that may indicate new CNS pathology that may need further investigation include (but are not limited to) visual disturbance, dysarthria, dysphasia, muscle strength, limb weakness, hyperflexia, paraparesis, micturition difficulty or urgency or incontinence, ataxia, neuropsychiatric or cognitive decline in excess of expectations based on the subject's recent history. Treatment-emergent abnormal neurologic findings should be reported as AEs.

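### TEAE incidence is stated as crude percentages within an exposure-dependent window, so accruing events would be modestly understated in whichever arm is stopped more; add exposure-adjusted columns beside n (%)

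*Protocol*

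**What the plan says.** Section 9.7.1.8.2 sets the measure: "The incidence of TEAEs will be reported as the number (percentage) of subjects with TEAEs by SOC and PT". The breakdowns by severity and relationship, and the tables for deaths, SAEs and TEAEs leading to discontinuation, take the same form. The window is tied to dosing, since the first limb of the definition reads "An AE that emerges during treatment within 4 weeks of the last dose of study drug", and "Only those AEs that are treatment-emergent will be included in summary tables". Collection runs longer: under section 9.5.1.5.1, AEs "should be collected beginning from the time the subject signs the study ICF through the last visit", which is Visit 15. Events after the window therefore appear only in listings.

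Exposure is summarized separately in section 9.7.1.8.1, by arm, in 3-month categories and as a total: "Overall exposure (number of subject-months) is defined as summation" over subjects. That total is not used as a denominator for any event.

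The stopping rules sit elsewhere. Under section 9.5.1.5.5, a subject with a moderate to severe rash, or any rash beyond 72 hours, "will be discontinued from study drug and a dermatologic consult will be requested regardless of whether the rash is considered drug related". Suspected drug rash and moderate to severe oral or genital herpes also end treatment. Under section 9.3.3, a first confirmed Grade 2 or greater lymphopenia leads to an interruption of 2 to 4 weeks. If a second is confirmed within 6 months, "then the subject should be discontinued permanently from the study drug".

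**The concern.** A subject stopped at month 6 is observed for about 7 months in the TEAE tables, yet counts as much in the denominator as one observed for 24. That is harmless if both arms lose time equally. Here the stops are triggered by events that section 7.1 reports for the drug. In the multiple-dose study, orolabial herpes relapse and drug rash were among the AEs of interest, and there was some CD4 reduction at 50 to 100 mg. This trial gives 50 mg. Shorter exposure on active drug is therefore foreseeable, though not established.

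If it happens, events that build up over two years, such as infections or cognitive decline reported as an AE, have less time to be counted on active drug. The error would favor the arm stopped more, in a study that section 7 describes as intended to be pivotal. Section 9.7.1.6.2 already uses Cox and Kaplan-Meier methods for the efficacy events, where the same problem of unequal follow-up arises.

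**Working it through.** **Figure in the plan.** The protocol gives no figure for this point. The nearest is the 30% dropout in section 9.7.2. It reproduces as a sample-size input: the difference is 0.25 × 1.75 = 0.4375, the SD is 2.05, and 90% power at two-sided 0.05 needs 462 per arm. Then 462/0.70 = 660 per arm, or 1320 in total, against the stated 1330. It is a single overall figure with no split by arm.

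**Assumptions.** Stopping proportions by arm (placebo vs active) of 28% vs 32%, 25% vs 35% and 20% vs 40%, each averaging 30%. Stopping times uniform over 24 months. Constant event hazard. True 24-month event risk p of 2%, 10% or 30%.

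**Formula.** With λ = −ln(1 − p)/24 per month, stopping proportion d and window w after the last dose:

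crude % = 1 − [ (d/24) ∫₀²⁴ exp(−λ(t + w)) dt + (1 − d) exp(−λ(24 + w)) ]

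**Worked case.** Take p = 10%, w = 0 and equal true hazards. λ = 0.00439. The average of exp(−λt) over 24 months is 0.1/(24 × 0.00439) = 0.949.
- d = 25%: 1 − (0.25 × 0.949 + 0.75 × 0.900) = 8.77%
- d = 35%: 1 − (0.35 × 0.949 + 0.65 × 0.900) = 8.28%
- Ratio: 8.28/8.77 = 0.944

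**Results over p = 2% to 30%.** Mean exposure, as a share of 24 months, is 1 − d/2.

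| Stopping, placebo vs active | Exposure ratio | True 1.00 appears as | Same, with 4-week window | True 1.25 appears as |
|---|---|---|---|---|
| 28% vs 32% | 0.84/0.86 = 0.977 | 0.98 | 0.98 | 1.18 to 1.22 |
| 25% vs 35% | 0.825/0.875 = 0.943 | 0.94 to 0.95 | 0.95 | 1.14 to 1.18 |
| 20% vs 40% | 0.80/0.90 = 0.889 | 0.89 to 0.90 | 0.89 to 0.90 | 1.08 to 1.11 |

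The last column is without the 4-week window.

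**Different stopping model.** With exponential stopping times, the 4-week window and a 10% event, the ratio is 0.97 (30% vs 35%), 0.94 (25% vs 35%) and 0.88 (20% vs 40%). Equal stopping gives 1.00. True hazard ratios of about 1.04, 1.07 and 1.14 respectively would be fully masked.

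**Early-onset events.** Now confine the hazard to the first 3 months, with 10% risk, no true difference, uniform stopping and the 4-week window.
- Crude ratio: 0.997 (25% vs 35%) and 0.994 (20% vs 40%).
- Expected time at risk, to first event or end of window: 19.9 vs 18.8 months, and 20.4 vs 18.3 months.
- Rate ratio: 0.997 × 19.9/18.8 = 1.05, and 0.994 × 20.4/18.3 = 1.11.

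For these events the percentage is nearly right and the rate is misleading. Under a constant hazard the reverse holds: the rate ratio recovers 1.00 and 1.25 exactly.

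**Lymphopenia interruption.** A single pause of 2 to 4 weeks is 2/104 to 4/104, or 1.9% to 3.8%, of the treatment period. Most of any loss would have to come from permanent stops.

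**The case against.** The strongest reply is that this is routine SAP content. The SAP is not among the documents at hand, the protocol nowhere says that n (%) will be the sole measure, and exposure-adjusted rates may be planned there. That limits the point to what section 9.7.1.8.2 states; an SAP that adds the rates would answer it.

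The crude percentage is also not false. It correctly describes how many treated subjects had an event under the regimen as given, stopping rules included. A rate answers a different question.

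Much is visible already. Exposure by arm (9.7.1.8.1), discontinuations and their reasons (9.7.1.3, 9.7.1.8.2) and by-visit laboratory shifts (9.7.1.8.3) are tabulated, so an imbalance would be seen. This stands as mitigation. However, total subject-months is not time to first event, and no planned table carries the imbalance into a comparison by SOC or preferred term.

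Three stronger readings should be resisted.
- A reader might infer that every other event is understated in the arm stopped more. The early-onset calculation shows otherwise. Rash and herpes are also counted before they trigger their own stop.
- A reader might infer that the active arm will have less exposure. The protocol gives no per-arm figure, the rash rule applies to both arms whatever the cause, and a first lymphopenia only interrupts dosing.
- A reader might conclude that the arm comparison should rest on rates. That trades a small bias for a larger one when events come early.

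**Conclusion.** The point holds in a limited form. The stated measure is a crude percentage within a window that closes 4 weeks after the last dose. If stopping differs between arms, it understates accruing events in the arm stopped more. The size is modest: about 2% on the ratio scale for a 4-point gap in stopping, 5% to 6% for 10 points, and 10% to 11% for 20 points. This rests on constant hazards and on assumed per-arm stopping proportions that the protocol does not supply. Equal stopping gives no bias, and events confined to the first 3 months lose at most about 0.6% in the two wider scenarios. It is a worthwhile improvement to a stated method, not an error that invalidates the safety tables, and it implies nothing about the stopping rules themselves.

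**What to change.** In section 9.7.1.8.2, or in the SAP with a reference from it:

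- Keep n (%). Beside it, for all TEAEs, SAEs and TEAEs leading to discontinuation, give subjects with a first event per 100 subject-years at risk. Time at risk runs to the first event or the end of the TEAE window.
- Add time-to-first-event cumulative-incidence curves by arm for rash, herpes and other infections, Grade 2 or greater lymphopenia, and abnormal dreams. The curves show whether events come early or accrue, and so which summary to trust.
- State that percentages, rates and curves are read together, and that rates do not replace the percentages in comparing arms, because a rate per subject-year assumes a constant hazard.

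The cost is a few extra table columns and four figures. Dosing dates and AE onset are already collected. No new data are needed and no clinical rule changes.

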9.7.1.8.3 LABORATORY VALUES

Laboratory results will be summarized using International System of Units, as appropriate. For all quantitative parameters listed in [Section 9.5.1.5.3](#), the actual value and the change from baseline to each postbaseline visit and to the end of treatment (defined as the last on-treatment value) will be summarized by visit and treatment group using descriptive statistics. Qualitative parameters listed in [Section 9.5.1.5.3](#) will be summarized using frequencies (number and percentage of subjects), and changes from baseline to each postbaseline visit and to end of treatment will be reported using shift tables. Percentages will be based on the number of subjects with both nonmissing baseline and relevant postbaseline results.

Laboratory test results will be assigned a low/normal/high (LNH) classification according to whether the value was below (L), within (N), or above (H) the laboratory parameter's reference range. Within-treatment comparisons for each laboratory parameter will be based on 3-by-3 tables (shift tables) that compare the baseline LNH classification to the LNH classification at each postbaseline visit and at the end of treatment. Similar shift tables will also compare the baseline LNH classification to the LNH classification for the highest and lowest value during the treatment period.

[Appendix 1](#) (Sponsor's Grading for Laboratory Values) presents the criteria that will be used to identify subjects with treatment-emergent markedly abnormal laboratory values (TEMAVs). Except for phosphate, a TEMAV is defined as a postbaseline value with an increase from baseline to a Grade of 2 or higher. For phosphate, a TEMAV was defined as a postbaseline value with an increase from baseline to a Grade of 3 or higher. When displaying the incidence of TEMAVs, each subject may be counted once in the laboratory parameter high and in the laboratory parameter low categories, as applicable.

